General Data Analysis Plan: All demographic and clinical variables with continuous measures will be expressed as means and standard deviations; categorical factors will be expressed as proportions. For non-normal data, the medians and inter quartile ranges will be displayed. The distribution of the continuous factors will be examined using the Kolmogorov-Smirnov test. For data that are normally distributed, the one-way ANOVA and Student's t-test will be used to compare groups of data. For data that are not normally distributed, the Kruskal-Wallis and Mann-Whitney tests will be used for comparisons. Chi-square and Fisher's exact tests will be used to analyze categorical data. For all comparisons, a value of $p < 0.05$ will be considered statistically significant.

Primary Outcome Analysis: Statistical analyses will be performed using SAS for Windows, version 9.2. Student's t-test will be used to compare post-operative pain scores for investigational and control subjects. Linear regression will be also be used to test the relationship between pain scores and regional anesthetic technique, while controlling for relevant clinical and demographic variables. Distance of first ambulation will be analyzed using Cox proportional-hazards model. Student's t-test will be used to compare patient and surgeon satisfaction.

Statistical Power and Sample Size Estimates : Sample size (50 each group) was determined using a Cohen's d table assuming a mean pain VAS score of 8 (SD = 3) on a scale of 0-10 for control subjects. A difference of VAS score of 3 between two study groups will be clinically relevant. A sample of 100 participants (50 patients per group) will have approximately 95% power to detect a reduction in pain score difference of 3 with significance level alpha of 0.05. We will perform an interim analysis after 50 patients have completed the study (25 patients in each group).

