surgery⁴. Recently, there has been increasing interest in the effectiveness of pain control with the use of quadratus lumborum blocks after THA . Currently, case reports have established a precedent regarding the efficacy of the QLB for THA^{5,6,10} in providing superior analgesia and decreasing verbal numerical pain scores, but randomized trials are still lacking. The goal of this study is to compare verbal numerical pain scores, post-operative pain medication (opioid) consumption, physical therapy scores, and patient satisfaction in patients that receive QLB versus no peripheral nerve blockade in patients undergoing THA. The results of this study have the potential to change the standard of care for patients undergoing THA.

b. Describe how outcomes will be measured for this protocol.

The primary end points are as follows:

1. Pain scores (numerical) will be obtained at immediate post op, 24 hours and 48 hours after surgery
2. Pain medication (opioid) use intraoperatively, as well as at 24 hours and 48 hours postoperatively
3. Physical therapist assessment of independence in mobility and transfers
4. Distance ambulated at 24 hours and 48 hours after surgery.

15. Background - in nontechnical, lay language

Summarize in 2-3 paragraphs past experimental and/or clinical findings leading to the design of this protocol. Include any relevant past or current research by the PI. For drug and device studies, summarize the previous results (i.e., Phase I/II or III studies).

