Currently, regional anesthesia techniques for total hip arthroplasty are limited. Fascia iliaca blocks (nerve blocks between the muscles of the hips) have been employed to provide analgesia for hip surgeries with blockade of the femoral, lateral femoral cutaneous, and obturator nerves via injection of local anesthetic in the iliacus fascia. In addition, lumbar plexus blocks have also been employed for post-operative analgesia, but the complexity of the block is high, and complications including epidural anesthesia are not infrequent. The quadratus lumborum block (QLB) is an abdominal truncal block in which local anesthetic is deposited into the thoracolumbar fascia (area between the muscle) or the quadratus lumborum muscle itself with the goal of providing analgesia to the ipsilateral T6 – L1 sensory dermatomes. It has already been demonstrated to provide effective post-operative analgesia for certain abdominal and pelvic surgeries⁷, but its use in total hip arthroplasty is limited to case reports.

The block is accomplished by locating the quadratus lumborum muscle, using a ultrasound probe. Local anesthetic is then injected. Cadaveric studies⁸ have demonstrated dye spread to the lumbar nerve roots and nerves within the transversus abdominis plane (TAP). Carney et al⁹ described a “posterior TAP” block, now known to be synonymous with QLB, that demonstrated contrast spread to the thoracic paravertebral space from T5-L1. Case reports have described analgesia in the corresponding sensory dermatomes after QLB⁴, and have demonstrated efficacy in patient undergoing THA^{5,6,10}. The QLB block has potential to cover lateral femoral cutaneous nerve, femoral nerve, obturator nerve and portions of lumbar plexus.

This study has been designed to investigate the efficacy of the QLB in providing post-operative pain control patients undergoing THA. Previous trials have demonstrated the effectiveness of the block for abdominal and pelvic surgeries, and case reports have shown its applicability in hip arthroplasty. In this randomized, controlled study we aim to compare QLB (block group) with control (control group) in patients undergoing THA with regard to verbal numeric pain scores (to be obtained when patient arrives to PACU & at discharge from PACU, then at 24 and 48 hours after surgery). The duration of analgesia, time to first opioid medication, physical therapy evaluations, time to discharge, and patient satisfaction scores will also be obtained.

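### Pain is scored three or four times per patient, but the plan names no deciding time point or summary and no method for repeated scores, so it defines no single error-controlled pain result

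*Combined protocol and SAP*

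**What the plan says.** Item 14.b lists pain first among the primary end points: "Pain scores (numerical) will be obtained at immediate post op, 24 hours and 48 hours after surgery". That is three scores per patient. Item 15 (Background) gives a different schedule, "to be obtained when patient arrives to PACU & at discharge from PACU, then at 24 and 48 hours after surgery", which is four.

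The Primary Outcome Analysis paragraph of the Statistical Considerations states that a "t-test will be used to compare post-operative pain scores for investigational and control subjects". It adds: "Linear regression will be also be used to test the relationship between pain scores and regional anesthetic technique", adjusted for clinical and demographic variables that it does not name. The General Data Analysis Plan supplies one-way ANOVA and the fallback "For data that are not normally distributed, the Kruskal-Wallis and Mann-Whitney tests will be used for comparisons", and applies p < 0.05 to every comparison.

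The sample-size paragraph takes one pain score per patient, "assuming a mean pain VAS score of 8 (SD = 3) on a scale of 0-10 for control subjects", with a relevant difference of 3 points, 50 patients per group and a test "with significance level alpha of 0.05". It does not say at which time that score is taken.

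The plan names no mixed model, generalized estimating equations, repeated-measures ANOVA, area under the curve or other per-patient summary.

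**The concern.** Scores from the same patient are correlated. Every method the plan lists for pain assumes independent observations. That is true of one score per patient at one time, and false of three or four scores per patient analysed together. The plan does not say which of these it will do. At least three analyses fit the text: a separate test at each time, one test or regression on all scores, and a test at a time point chosen later. They have different error rates and answer different questions.

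At stake is whether a p-value below 0.05 for pain, the first-listed primary end point, carries the 5% error rate that the plan states. Separate tests also leave no single estimate of the effect on pain, and each drops any patient who lacks that score, without using the patient's other scores.

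**Working it through.** **Inputs from the documents.** Scores per patient: m = 3 (item 14.b) or m = 4 (item 15). From the sample-size paragraph: 50 per group, SD 3, difference 3, alpha 0.05 (sidedness not stated; two-sided assumed).

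**Assumed input.** The documents give no within-patient correlation ρ. It is taken as equal between all pairs of times and shown at 0.3, 0.5 and 0.7.

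**Step 1: the plan's own power figure.** The plan states about 95%. The standardised difference is 3/3 = 1. The normal approximation gives Φ(1 × √(50/2) − 1.96) = Φ(3.04) = 99.88%, and the noncentral t gives 99.86%. The stated figure does not reproduce. That is a separate matter; what counts here is that power for one score per patient is already close to 100%.

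**Step 2: separate t-test at each time, each at 5%.** Patients are independent at a given time, so each test keeps its 5%. With independent tests, the chance of at least one false positive would be 1 − 0.95³ = 14.3% or 1 − 0.95⁴ = 18.5%. With correlated scores, from 40,000 simulated null trials of 50 per group:

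| ρ | three times | four times |
|---|---|---|
| 0.3 | 13.7% | 17.7% |
| 0.5 | 12.3% | 15.5% |
| 0.7 | 10.8% | 13.1% |

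**Step 3: all scores pooled as independent.** The true variance of the group difference exceeds the assumed variance by DE = 1 + (m − 1)ρ, so type I error = 2 × [1 − Φ(1.96/√DE)]. With m = 3 and ρ = 0.5, DE = 2.0 and 1.96/√2 = 1.386, which gives 16.6%.

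| ρ | DE, m = 3 | error | DE, m = 4 | error |
|---|---|---|---|---|
| 0.3 | 1.6 | 12.1% | 1.9 | 15.5% |
| 0.5 | 2.0 | 16.6% | 2.5 | 21.5% |
| 0.7 | 2.4 | 20.6% | 3.1 | 26.6% |

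Simulation agrees to within about 0.3 percentage points.

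These figures assume that mean pain is the same at every time. If it is not, a pooled test without time in the model counts the change over time as error, and the inflation shrinks. As an illustration (assumed), let the time means vary with SD 1.5. The apparent variance is then 9 + 2.25 = 11.25, and the inflation factor at m = 3, ρ = 0.5 is 2.0 × 9/11.25 = 1.6, so the error is 12.1% instead of 16.6%.

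**Step 4: patient as the unit.** A t-test on each patient's mean score held 4.7%–5.1% in the same simulations.

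**Step 5: does splitting cost power?** The mean of m scores has variance DE/m relative to one score: 0.53–0.80 for m = 3 and 0.48–0.78 for m = 4.

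- At the planned 3 points, power is 99.86% for one time point and at least 99.98% for the mean. The gain is negligible.
- At a constant 1.5 points (an assumed value, not in the plan), power is 70% for one time point and 79%–92% for the mean of three.
- If the effect wanes as 1.5, 0.75 and 0 points (assumed), the average effect is 0.75. At ρ = 0.5 its power is about 33%, against 70% at the first time alone.

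So averaging helps for a smaller, sustained effect and can hurt for a waning one.

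**The case against.** The best defence is that the plan never says it will pool. It compares subjects, and it sizes the trial on one score for each of 50 patients per group, so one comparison per time point is the natural reading. On that reading each t-test is valid. With complete data and no covariates, a mixed model with unstructured covariance would give the same estimate at each time. All of this stands.

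A reader might infer that the plan's type I error is 12%–27%, or that its t-test is invalid because the scores are correlated. The documents do not support either inference. Those figures need pooling, which the text allows but does not state, together with an assumed correlation and a flat time course. A reader might also infer that testing times separately leaves the trial short of power. At the plan's own 3-point difference it does not.

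It can also be said that naming one time point or one per-patient summary would make the planned t-test sufficient. That is correct for error control. The mixed model adds the use of patients with partial data, and one framework for both the adjusted effect and the time course. How much the partial data would matter cannot be sized, because the documents give no rate of missing scores.

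The defence does not answer the central gap. Even on the natural reading there are three or four unadjusted tests, no rule for which one decides, and two conflicting lists of times.

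**Conclusion.** The concern holds as a gap in specification: the text does not lead to one error-controlled pain result. On the natural reading, the chance of at least one false-positive pain finding is about 11%–14% (three times) or 13%–18% (four), against a nominal 5%. If scores were pooled as independent, type I error would be up to about 12%–21% or 16%–27%.

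All these ranges rest on an assumed correlation of 0.3–0.7. The pooled ranges also rest on a flat time course, and are lower otherwise. Any positive correlation inflates a pooled test when the time course is flat. The multiplicity of separate tests is present at any correlation short of perfect. Precision is a secondary argument that matters only for effects smaller than planned. The sponsor should make the change, since it affects a primary end point and costs little.

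**What to change.** 1. Reconcile items 14.b and 15 on when pain is scored, in particular whether the PACU contributes one score or two.
2. Replace the t-test and the ordinary regression for pain with one linear mixed model: arm, time, arm-by-time and baseline covariates named in advance, unstructured within-patient covariance, and all available scores.
3. Name one contrast beforehand, either the arm difference at one stated time or the average over the postoperative times, as the single pain test at alpha 0.05. The choice should reflect whether the effect of a single preoperative injection is expected to last or to wane.
4. Report the other per-time differences with 95% confidence intervals as secondary.

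The cost is a few lines of SAP text and SAS code, with no new data or visits. The downside is that only one contrast carries the confirmatory claim for pain. The change settles multiplicity within pain only; item 14.b lists other primary end points, and this step does not address them.

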16. Participants (Screening and Selection)

- a. How many participants are to be enrolled at UAB (if other sites relying on UAB IRB, list the number for each site)? **100**
If multi-site study, total number at all sites/institutions: **N/A**
- b. Describe the characteristics of anticipated or planned participants (if multiple groups, repeat list for each group).
Sex: **M,F**
Race/Ethnicity: **any**
Age: **>18 years**
Health status: **American Society of Anesthesiologist (ASA) Physical Status Score 1, II, or III**
- c. From what population(s) will the participants be derived? **All patients scheduled for total hip arthroplasty are scheduled in the preoperative assessment clinic days to weeks prior to their surgery. Study participants will be derived from this population.**

Describe your ability to obtain access to the proposed population that will allow recruitment of the necessary number of participants: **Before total hip arthroplasty, all patients report to the Highlands Preoperative assessment Clinic (HPAC) for standard of care preoperative assessment and examination and preoperative testing, tailored to patient comorbidities. This is not a service that will be billed additionally for study participants, as it is standard of care for all total hip arthroplasty patients, regardless of participation in the study. During this visit they will be given a “Patient Information Sheet,” describing the study. On the day of surgery, patients scheduled for surgery will be seen in the preoperative holding area and enrolled in the study if they choose and are appropriate candidates.**

- d. Describe the inclusion/exclusion criteria:

Inclusion Criteria: Patients undergoing total hip arthroplasty under spinal anesthesia. Adults, 18 years of age or older. Patients classified by the American Society of Anesthesiology (ASA) class I, II, or III.

Exclusion Criteria; Any patient not classified as an ASA I, II, or III. Those who are allergic or intolerable to local anesthetics. Patients with pre-existing neurologic or anatomic deficiency and lower extremity on the side of the surgical site, or patients with coexisting coagulopathy. Patients that are pharmacologically anticoagulated will be excluded if placement of peripheral nerve block would be contraindicated according to ASRA (American Society for Regional Anesthesia) guidelines or if spinal anesthesia would be contraindicated according to ASRA guidelines.

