A. Participants in the study will be randomly assigned to either receive the pain block ("block group") or not ("control group"). The patient will be blinded and thus unaware of the group that they have been assigned. The patients are receiving sedation, including fentanyl and midazolam, an amnestic, prior to ultrasound scanning and +/- block placement. The amnestic properties of sedation will serve as blinding for the procedure. In the postoperative survey, we

ask the patients which group they believe they were in, which will help assess the adequacy of the blinding.

- a. **Block group: Subjects that are in the block group will receive the pain block while they are in pre-operative holding. The block will be administered as follows:**
 - i. **The patient will be placed on their side. Standard of care noninvasive monitors will be used, and oxygen will be given by nasal cannula. Midazolam and fentanyl will be given to patient comfort. Note: midazolam and fentanyl are provided to all patients who are receiving this surgery and is not part of this research project. The timing of the delivery of this medication may differ than standard of care, but the doses and indications are the same. Skin will be prepped and draped as per standard of care.**
 - ii. **Using ultrasound guidance, we will locate the appropriate space for the block. We will first inject numbing medication called lidocaine under the patient's skin (1-2 mL of 1% lidocaine; 10-20 mg). Then, we will inject another numbing medication called bupivacaine (30 mL of 0.25% bupivacaine with 1:400,000 epinephrine; 75 mg bupivacaine and 75 mcg epinephrine) between muscles using a syringe and needle.**
 - iii. **After the block is placed, patients will have their surgery performed.**
- b. **Control group: Patients randomized to the control group will be treated in the same manner (as described in section "i" above) as those randomized to the block group. The ultrasound probe will be used to identify the quadratus lumborum muscle, similar to patients in the block group. However, no local anesthetic will be injected.**

B. Postoperative data will be collected for both groups by a blinded study team member listed on this protocol.

- a. **Post-operative data that will be collected is listed in the attached Case Report Form.**
- b. **Information obtained from the patient will be collected using the attached Patient Interview Script.**
- c. **Patient will be followed up until nerve block resolves.**

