- d. **The hours from block placement until hospital discharge will be calculated.**

b. What is the probable length of time required for the entire protocol (i.e., recruitment through data analysis to study closure)? **One year.**

c. What is the total amount of time each participant will be involved? **Each participant will be involved in the study for approximately 48 hours. Each procedure time period is listed below.**

d. If different phases are involved, what is the duration of each phase in which the participants will be involved? If no phases are involved, enter "None." **None**

e. List the procedures, the length of time the procedure takes, the total # of times the procedure is performed, and indicate whether each is performed solely for research or would already be performed for treatment or diagnostic purposes (routine care) for the population.

-Insert additional table rows as needed.

-If procedure is sometimes research and sometimes routine care, include on separate lines with number of times as each.

Procedure	Length of Time Required of Participants	Frequency of Repetition	Research (Res) – OR- Routine Care
Pre-surgical Evaluation on the day of surgery	30 minutes	once	 Res  Routine
Randomization on day of surgery	5 minutes	Once	 Res  Routine
Placement of block	Approximately 30 min.	Once	 Res  Routine
Post Anesthesia Care Unit (PACU) assessment	10 minutes	Once	 Res  Routine
First postoperative assessment survey (approximately 24 hours after surgery)	10 minutes	Once	 Res  Routine
Second postoperative assessment survey (approximately 48 hours after surgery)	10 minutes	Once	 Res  Routine

- f. Will an interview script or questionnaire be used? Yes No
If Yes, attach a copy.
- g. Will participants incur any costs as a result of their participation? Yes No
If Yes, describe the reason for and amount of each foreseeable cost. _____
- h. Will participants be compensated? Yes No
If Yes, complete i-v.
i. Type: (e.g., cash, check, gift card, merchandise): _____

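### No preoperative pain score is listed, so the adjusted pain regression has no scheduled baseline value of its own outcome; one question before sedation would buy precision cheaply

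*Combined protocol and SAP*

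**What the plan says.** Item 14.b, first end point: "Pain scores (numerical) will be obtained at immediate post op, 24 hours and 48 hours after surgery". Item 15 gives the pain times slightly differently: "to be obtained when patient arrives to PACU & at discharge from PACU, then at 24 and 48 hours after surgery". Neither list has a time before surgery.

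The table in item 17.e has an entry "Pre-surgical Evaluation on the day of surgery", a single 30-minute contact marked as routine care, with no content itemised. Its three study assessments fall in the PACU and at about 24 and 48 hours. Item 16.c describes an earlier clinic visit for "standard of care preoperative assessment and examination and preoperative testing, tailored to patient comorbidities", again without mention of a study pain score. On data capture, item 17 says: "Post-operative data that will be collected is listed in the attached Case Report Form". That form, and the interview script cited with it, are attachments that are not in the text.

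Under Primary Outcome Analysis, "Student's t-test will be used to compare post-operative pain scores for investigational and control subjects". A linear regression of pain on anesthetic technique is then added, "while controlling for relevant clinical and demographic variables". No covariate is named, and nothing says when a covariate must have been measured.

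**The concern.** The plan commits to a covariate-adjusted pain analysis, but the text schedules no pre-treatment value of the outcome being adjusted. Patients who arrive with more hip pain may report more pain afterwards. To the extent that they do, the difference between patients stays in the error term and widens the interval for the block effect. A chance difference between arms in preoperative pain also cannot be taken out of the estimate. A standardized score not asked before sedation cannot be collected later.

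The unrestricted covariate wording adds a smaller matter. The block is given before surgery and intraoperative opioid use is itself an end point (item 14.b), so the wording would allow adjustment for something the block may have changed.

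**Working it through.** **Is a baseline score scheduled?** The end-point list (item 14.b), the background (item 15) and the procedures table (item 17.e) agree that pain is scored only after surgery. The text supports the statement that no preoperative score is listed, and no more than that.

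**Could one be taken?** Item 5.b puts consent in a private preoperative room, with transfer to the block area after enrollment and randomization. Item 16.j puts the eligibility check in the same holding area. Item 17 gives sedation before scanning. There is therefore a point before both sedation and allocation.

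**Inputs from the plan:** SD 3 ("assuming a mean pain VAS score of 8 (SD = 3) on a scale of 0-10 for control subjects"), 50 per arm, target difference 3 points, alpha 0.05. Sidedness is not stated; I take two-sided.

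**The plan's own power figure.** The unadjusted standard error is 3 × sqrt(2/50) = 3 × 0.20 = 0.600. The noncentrality is 3/0.600 = 5.0 on 98 degrees of freedom. Power is 99.86% by noncentral t (99.88% by the normal approximation). The stated figure of about 95% does not reproduce; it corresponds to about 27 per arm. That mismatch is a separate matter and does not decide this point.

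**Effect of the covariate.** Let r be the correlation of preoperative with postoperative pain. The documents give no r, so 0.1 to 0.5 is an assumed range.

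- Residual variance factor: 1 − r²
- SE = 0.600 × sqrt(1 − r²)
- 95% half-width = t(0.975) × SE, with 98 degrees of freedom unadjusted and 97 adjusted
- Equivalent total sample = 100/(1 − r²)
- Power by noncentral t with noncentrality 1.5/SE. The 1.5 points is my assumption, half the difference that the plan calls clinically relevant.

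| r | 1 − r² | SE | Half-width | Equivalent N | Power, 3 points | Power, 1.5 points |
|---|---|---|---|---|---|---|
| unadjusted | 1.00 | 0.600 | 1.191 | 100 | 99.86% | 69.7% |
| 0.1 | 0.99 | 0.597 | 1.185 | 101 | 99.87% | 70.1% |
| 0.3 | 0.91 | 0.572 | 1.136 | 110 | 99.94% | 73.7% |
| 0.5 | 0.75 | 0.520 | 1.031 | 133 | 99.99% | 81.6% |

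The half-width falls by 0.055 points at r = 0.3 (1.191 − 1.136) and by 0.160 at r = 0.5 (1.191 − 1.031). At r = 0.1 the gain is negligible.

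**Chance imbalance.** The standard error of the difference between arms in baseline pain is sqrt(2/50) = 0.20 SD. An imbalance of twice that, 0.40 SD, shifts the unadjusted pain difference by 0.40 × r × 3: 0.36 points at r = 0.3 and 0.60 at r = 0.5. The unadjusted standard error already allows for such shifts on average; ANCOVA removes the one that actually occurred.

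**The case against.** The strongest reply is that the plan does not need this. On its own inputs, unadjusted power for the 3-point target is 99.9%, and the half-width of 1.19 is well under half of that target. The gain rests on a correlation that nobody has supplied. It may be low for the PACU scores in particular, since all patients have spinal anesthesia. All of this stands, and it limits the point to an inexpensive improvement.

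The t-test is listed first and the regression is additional, so a better covariate would leave the first-listed result unchanged. That also stands, and it is why the fix has to say which analysis is the main one.

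Several stronger readings are tempting, and the documents do not support them:

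- *That the regression cannot include preoperative pain.* The Case Report Form is not shown, and a routine preoperative record may hold a score. Such a score would still not be one that the text schedules or standardizes.
- *That the pain comparison is biased.* Allocation is randomized 1:1 (item 16.e), so the unadjusted test is valid.
- *That nothing can be recovered later.* Other prognostic variables in the planned regression may recover some precision.
- *That the regression will adjust for post-randomization variables.* The wording permits it but does not plan it.
- *That surgeon must be a covariate.* Item 16.h refers to surgeons in the plural, but gives neither their number nor any sign of a surgeon effect.

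**Conclusion.** The point holds as one of efficiency. The available text lists no preoperative pain score, and the planned adjusted analysis would be better with one. The gain in half-width runs from practically nothing at r = 0.1 to about 13% at r = 0.5 (1.031/1.191 = 0.87), the latter worth about a third more patients. It matters for the width of the interval and for differences smaller than 3 points, not for detecting the planned effect.

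These figures assume SD 3, 50 analysed patients per arm, two-sided alpha of 0.05, a linear relation, and one correlation for whichever time point is analysed. They leave out the small cost of estimating the slope, about one degree of freedom in 98, which roughly offsets the 1% variance gain at r = 0.1. Nothing here shows that the trial's conclusion would change. The case for acting is that the cost is very small and a missed score cannot be collected afterwards.

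**What to change.** - Record one 0-10 verbal hip-pain score in preoperative holding, after consent, before sedation and before allocation is known. Add it to the schedule in item 17.e and to the data form, or, if the Case Report Form already carries such a score, say so in the text.
- In the Primary Outcome Analysis, make the main pain analysis an ANCOVA of postoperative pain on group with that score as a named covariate. Keep the t-test as supportive.
- State that any further covariates are named in advance and measured before randomization.

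The cost is one question, one data field, a few lines of SAP wording and a minor amendment to the IRB form. The sample size does not change. The question has to be in place before patients are treated, because those already treated cannot supply the score.

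### The Cox model is assigned to a first-walk distance that is not the declared walking end point, and a hazard ratio would not give a difference in distance

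*Combined protocol and SAP*

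**What the plan says.** Item 14.b introduces four outcomes with "The primary end points are as follows". The fourth is "Distance ambulated at 24 hours and 48 hours after surgery".

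The Statistical Considerations deal with walking in one sentence, under Primary Outcome Analysis: "Distance of first ambulation will be analyzed using Cox proportional-hazards model". They give no origin, event or censoring rule.

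The General Data Analysis Plan supplies default tests: "For data that are normally distributed, the one-way ANOVA and Student's t-test will be used to compare groups of data" and "For data that are not normally distributed, the Kruskal-Wallis and Mann-Whitney tests will be used for comparisons". It also has continuous clinical variables summarised by mean and standard deviation, or by median and interquartile range when not normal. It does not ask for a confidence interval for a between-group difference.

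Item 15 adds further outcomes: "The duration of analgesia, time to first opioid medication, physical therapy evaluations, time to discharge, and patient satisfaction scores will also be obtained". Time to first walking is not named among them. Item 17 refers to a form for the detail: "Post-operative data that will be collected is listed in the attached Case Report Form". That form is not in the supplied text.

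**The concern.** The analysis sentence and the end point name different variables: the distance of a single first walk, and distance at two fixed times. The method fits neither without further definition. A Cox model needs an axis along which patients are followed and an event that ends follow-up. A walked distance is simply recorded.

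Two things are at stake. First, a declared primary end point may be reported on a scale that does not answer how much further block patients walked. Second, the direction of benefit depends on an axis that the plan leaves open. With distance as the axis, the event is stopping, so a hazard ratio below 1 means that block patients walked further. With time as the axis, the event is the first walk, so a hazard ratio below 1 means that they walked later. Whoever fits the model will know which axis was used, but a reader of the result may not.

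**Working it through.** The plan gives no figure for distance. Its sample-size statement concerns pain only, so there is nothing to reproduce on this point. The check is a comparison of the text, followed by an illustration on assumed inputs.

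**Step 1: the possible readings of the Cox sentence.**

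| Reading | Consequence for the Cox sentence | Consequence for the fourth end point |
|---|---|---|
| It is meant for the fourth end point | Variable misnamed; no event or censoring defined | Effect measure is a hazard ratio, not a distance |
| It means a separate first-walk distance | Outcome not listed in item 14.b or item 15 | Left to the general t-test/Mann-Whitney rule |
| Distance is a slip for time | Time to first walk is not listed in item 14.b or item 15; no origin or censoring rule | Left to the general t-test/Mann-Whitney rule |

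The text needs reconciling on every reading.

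**Step 2: what a hazard ratio (HR) says about distance (illustration, all inputs assumed).** Take Weibull distances with common shape k, so that S(d) = exp(-(d/λ)^k). Under proportional hazards the treated scale is λ × HR^(-1/k). The ratio of mean distances, block to control, is therefore HR^(-1/k).

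| | k = 1 | k = 1.5 | k = 2 | k = 3 |
|---|---|---|---|---|
| Mean gain at HR 0.60, i.e. 0.60^(-1/k) - 1 | 66.7% | 40.6% | 29.1% | 18.6% |
| Same, on an assumed control mean of 30 units | 20.0 | 12.2 | 8.7 | 5.6 |
| HR produced by a 50% gain, i.e. 1.5^(-k) | 0.667 | 0.544 | 0.444 | 0.296 |

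One hazard ratio corresponds to very different gains, and one gain to very different hazard ratios.

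**Step 3: the same point with another positive distribution.** Distances were simulated as lognormal, 20,000 per arm, with the median rising from 30 to 45. Fitted hazard ratios were 0.276, 0.511 and 0.640 at coefficients of variation of 0.3, 0.6 and 1.0. Replacing each distance d by log(1 + d) left all three unchanged. The estimate uses only the ordering of the distances and carries no information in units walked.

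**Step 4: what a difference would give.** With 50 per arm, all measured, and a common standard deviation (SD), the 95% confidence interval for a mean difference has half-width t(0.975, 98) × √(2/50) × SD = 1.984 × 0.2 × SD = 0.397 SD. For assumed SDs of 15, 25 and 40 units that is about 6, 10 and 16 units. It widens if fewer patients are measured at 48 hours.

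**The case against.** The strongest reply is that little is lost in practice, and several parts of it stand.

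- **Distances would still be shown.** A reader might infer that the report would contain no walking distances. The descriptive rule for continuous clinical variables does not support that: per-arm summaries would appear. What is missing is an estimated difference with its interval.
- **The end point is not without a method.** A reader might infer that the fourth end point has no planned analysis. The general rule covers it, and it is not alone in depending on that rule: opioid use and the physical therapist's assessment have no specific line either.
- **The test is not invalid.** A reader might infer lost power or false positives. The documents do not support this. Cox regression on positive, fully observed distances is a valid rank-type test. The sample size rests on pain, whose analysis is untouched.
- **Placement proves little.** The same paragraph covers patient and surgeon satisfaction, which item 14.b does not list. Its heading therefore does not show that the Cox sentence is meant for the fourth end point.
- **The sentence may be a slip for time to first walking.** That is plausible, but the supplied text does not say so. Item 15 mentions physical therapy evaluations without itemising them, and the Case Report Form is not supplied, so a definition there cannot be excluded. Even so, the outcome would need listing, and distance would still lack its own line.

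The magnitude figures are also fairly called illustration, since no input comes from the documents. None of this removes the mismatch between the two sections.

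**Conclusion.** The point stands as a mismatch of variable and effect measure that should be corrected. The Statistical Considerations name a walking variable that is not the declared end point and attach a model for which no event or censoring is defined. That conclusion rests on the text alone and is firm.

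Which consequence follows depends on what the sentence was meant to say, and the documents do not settle that. If it was meant for the fourth end point, the planned estimate cannot state a difference in distance. The assumed Weibull cases show a hazard ratio of 0.60 compatible with mean gains of 19% to 67% for shapes 3 to 1. If it was meant for something else, an unlisted outcome is analysed and the end point keeps only the general rule.

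**What to change.** Reconcile Primary Outcome Analysis with item 14.b:

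1. Replace the Cox sentence with a between-group comparison of distance at 24 hours and at 48 hours, using the plan's t-test/Mann-Whitney rule. Report the difference with a 95% confidence interval: a mean difference, or the Hodges-Lehmann shift where Mann-Whitney is used. The Hodges-Lehmann estimate would be new to the plan.
2. Count patients who are in hospital and assessed but do not walk as zero, and report their number per arm.
3. Do not set patients discharged before the time point to zero. Item 18 names earlier discharge as a hoped-for benefit, so a zero could penalise good recovery. Treat them as not measured and report their number per arm. Their last recorded distance before discharge can serve as a sensitivity analysis.
4. If a first-walk distance was intended, list it as an outcome and compare it by the same rule, in addition to distance at 24 and 48 hours.
5. If time to first walking was intended, list it as an outcome and keep Cox for it with a stated origin, event and censoring rule. Add the separate line for distance.

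The cost is a small amount of extra wording. The sponsor should also check that the Case Report Form records distance at both times and distinguishes patients who did not walk from those already discharged.
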